JRMO Non-CTIMP Protocol Template

- 16. MONITORING & AUDITING (if applicable)
- 17. TRIAL COMMITTEES
- 18. FINANCE AND FUNDING
- 19. INDEMNITY
- 20. DISSEMINATION OF RESEARCH FINDINGS (if applicable)
- 21. REFERENCES
- 22. APPENDICES

2. GLOSSARY of Terms and Abbreviations

AE	Adverse Event
AR	Adverse Reaction
ASR	Annual Safety Report
CA	Competent Authority
CI	Chief Investigator
CRF	Case Report Form
CRO	Contract Research Organisation
DMC	Data Monitoring Committee
EC	European Commission
GAfREC	Governance Arrangements for NHS Research Ethics Committees
ICF	Informed Consent Form
JRMO	Joint Research Management Office
NHS REC	National Health Service Research Ethics Committee
NHS R&D	National Health Service Research & Development
Participant	An individual who takes part in a clinical trial
PI	Principal Investigator
PIS	Participant Information Sheet
QA	Quality Assurance
QC	Quality Control
RCT	Randomised Controlled Trial
REC	Research Ethics Committee
SAE	Serious Adverse Event
SDV	Source Document Verification
SOP	Standard Operating Procedure
SSA	Site Specific Assessment
TMG	Trial Management Group
TSC	Trial Steering Committee

4. SUMMARY/SYNOPSIS

Short Title	SPM regulation by Fish Oil Supplements in Healthy Volunteers
Methodology	A randomised, double-blind, placebo-controlled study to determine whether fish oil supplementation regulates peripheral levels of specialized pro-resolving mediators and white blood cell responses in healthy volunteers
Research Sites	Barts and The London School of Medicine Queen Mary University of London William Harvey Research Institute [name]
Objectives/Aims	The objective of this study is to learn more about the biology of fish oil supplementation in human healthy volunteers by assessing the actions of these supplements in healthy volunteers.
Number of Participants/Patients	40
Main Inclusion Criteria	Able to provide informed consent, willingness to abstain from fish for 2 days before each study visit, physical examination, laboratory tests.
Statistical Methodology and Analysis (if applicable)	The results will be tabulated and assessed for biological activity of the fish oil supplement and any relationship between dose and primary variables. Because the study is exploratory in nature, there will be no formal statistical analysis of the data.
Proposed Start Date	July 2016
Proposed End Date	April 2016
Study Duration	9 months

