9.3 Sample Size

Power calculations were conducted using data obtained from published studies where healthy volunteers were given 1 mg essentially (from a different source to that being investigated in the present study) and peripheral blood lipid mediator levels were evaluated pre-essential fatty acid and 4 hours after supplement intake (Colas et al Reference 17). Using pre and post values of 10 mediators values from these studies and Wilcoxon matched-pairs signed rank test a sample size of 33 participants is required to detect a threefold odds of an increase in post value when compared with the pre value with a power of 80% at the 5% level of statistical significance using the formulae from reference 18. Fifty mediators will be examined and it is recognized that at the 5% level of statistical significance around 2-3 mediators will falsely be identified as having significant changes. However the functional effect of all significant mediators will be subsequently examined by assessing white blood cell function, including the ability of peripheral white blood cells to phagocytose bacteria and the response of peripheral white blood cells and platelets to an inflammatory stimulus. If we do not observe increases in the ability of peripheral white blood cells to phagocytose bacteria and/or decreases in the activation of peripheral white blood cells and platelets then these mediators will be assumed to be false positive results. For these analysis the white blood cell function and peripheral blood lipid mediator levels at the 2h and 4h intervals post essential fatty acid/placebo administration will be compared to pre-supplementation values. The time point and dose that give the greatest change in all the mediators and the greatest regulation of peripheral white blood responses will be judged to be the main outcome measure for future trials.

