9.4 Statistical Analysis Plan

Wilcoxon matched-pairs signed rank test will be used to analyse the pre and post values of 10 mediators as well as white blood cell function (at 2 and 4h). The time point corresponding to the greatest number of the mediators being statistically significantly different from their pre-test values at the 5% level of statistical significance will be identified as the time point of interest. At the 5% level of significance testing 50 mediators will result in at least 2-3 associations being falsely statistically significant. Thus, the functional effect of all significant mediators will be subsequently examined by assessing white blood cell function, including the ability of peripheral white blood cells to phagocytose bacteria and the response of peripheral white blood cells and platelets to an inflammatory stimulus to determine if the identified associations are likely to be true changes. If we do not observe increases in the ability of peripheral white blood cells to phagocytose bacteria and/or decreases in the activation of peripheral white blood cells and platelets then these mediators will be assumed to be false positive results. Values at different times will not be compared just the value at each time point will be compared to the same person's pre test values.

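### The synopsis rules out formal analysis while Section 9 plans powered 5% tests, and the Section 9 tests never compare a dose with placebo or with another dose

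*Combined protocol and SAP*

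**What the plan says.** **Synopsis (Section 4).** "The results will be tabulated and assessed for biological activity of the fish oil supplement and any relationship between dose and primary variables". The next sentence reads: "Because the study is exploratory in nature, there will be no formal statistical analysis of the data".

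**Section 9.3.** From earlier pre/post data, "a sample size of 33 participants is required to detect a threefold odds of an increase in post value when compared with the pre value". The stated power is 80% and the stated level 5%; the formulae are given only by citation. The section then compares 2h and 4h values after supplement or placebo with the pre-dose values. It ends with a rule: the time point and dose showing the largest change in mediators and cell responses become the main outcome measure for future trials.

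**Section 9.4.** "Wilcoxon matched-pairs signed rank test will be used to analyse the pre and post values of 10 mediators as well as white blood cell function". These tests use the 2h and 4h values. The time point of interest is the one with the most mediators significant at 5%. Dose is not mentioned. The section closes: "Values at different times will not be compared just the value at each time point will be compared to the same person's pre test values".

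**Elsewhere.** Section 7.4 describes a placebo-controlled crossover meant to find the dose that raises SPM levels. It gives placebo the job of checking diurnal variation, which it calls currently unknown, and makes each volunteer their own control for each dose. Under Section 8.3 every participant receives placebo and all three doses. Section 8.11 sets a per-protocol primary and an intention-to-treat secondary analysis.

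**The concern.** There are two linked problems.

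First, the plan says both that there will be no formal analysis and that there will be powered significance tests. Nothing in the document says which text prevails. A reader of the results cannot tell what standing a p-value below 0.05 was meant to have. This matters because the plan itself expects 2-3 false positives among 50 mediators.

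Second, the design randomises each person through placebo and three doses, but no named test uses that. Section 9 contains no dose-minus-placebo comparison, no comparison between doses and no dose trend. What is at stake is the attribution of any rise to the supplement, and the choice of dose carried into future trials.

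**Working it through.** **1. Is Section 9 a real test plan?** Its sample size can be reproduced, so it is.

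Inputs from Section 9.3: threefold odds of an increase, 80% power, 5% level. Sidedness is not stated.

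- Probability of an increase: p = 3/(1+3) = 0.75.
- Two-sided sign test: n = (1.960 + 0.842)² / [4(0.75 − 0.5)²] = 7.849/0.25 = 31.4, so 32. Dividing 31.4 by 0.955 gives 32.9, so 33.
- Two-sided one-sample proportion formula with continuity correction: 32.8, so 33.
- Noether's signed rank formula, with 0.75 as its probability: n = (z sum)² / [3(0.25)²]. Two-sided this is 7.849/0.1875 = 41.9, so 42. One-sided it is 33.0, so 33.
- Exact two-sided sign test at n = 33: reject at 23 or more increases (or 23 or more decreases); actual level 3.5%, power 81.9%.

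The stated 33 follows under several standard conventions, though not all. The false-positive figure also checks: 50 × 0.05 = 2.5. A powered plan at the 5% level cannot stand beside a statement that there will be no formal analysis.

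**2. What can the named tests show?** Write the change from 0h to time t in a cycle at dose d as:

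- supplement cycle: S(d,t) + D(t)
- placebo cycle: D(t)
- difference: S(d,t)

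Here S is the supplement effect and D is everything else that moves between 0h and t, including time of day. The Section 9.4 test asks whether S + D is zero. Only the difference from placebo isolates S, and that difference is not in the plan.

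**3. How large could the error be?** The documents give no figure for D, so the following is an assumption shown over a range. Let S = 0, and let q be the probability that a mediator rises through time of day alone. The chance of a significant rise on the exact sign test is P(X ≥ 23 | n = 33, q), or P(X ≥ 27 | n = 40, q):

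| q | n = 33 | n = 40 |
|---|---|---|
| 0.50 | 1.8% | 1.9% |
| 0.60 | 16.9% | 21.1% |
| 0.65 | 35.7% | 44.1% |
| 0.70 | 59.9% | 70.3% |
| 0.75 | 81.9% | 89.7% |

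The sign test stands in for the Wilcoxon test because the plan states its effect as odds of an increase. With no time-of-day effect (q = 0.50) the error is controlled. It climbs quickly as q moves away from one half.

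**4. What does the greatest-change rule do?** One dose always has the largest observed change. If the three doses behave identically, each is named with probability 1/3. The rule carries no estimate of the difference between doses and no measure of uncertainty. It also does not say how changes in many mediators and several cell responses combine into one largest change.

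**5. Is the comparison available?** Yes. In the Section 8.3 table each of the four treatments appears twice in every cycle across the eight groups. Every participant has a 0h sample in every cycle. Dose-minus-placebo differences can be formed within person with periods balanced.

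**The case against.** **Section 9 does address dose.** This stands in part. Section 9.3 has a dose-selection rule, so a reader who inferred that Section 9 ignores dose, or that neither text speaks to the aim in Section 7.4, would go too far. If the pre/post tests were run separately by dose, they and the rule would address the aim, though weakly. What is missing is any comparison against placebo or between doses.

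**The dose texts do not exclude each other.** This stands. The synopsis promises to tabulate and assess "any relationship between dose and primary variables", which is descriptive and compatible with Section 9. The closing sentence of Section 9.4 excludes comparisons between times; it does not forbid comparisons between doses. On dose the fault is a gap in specification. Only the sentence ruling out formal analysis is a contradiction.

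**Exploratory studies may use tests.** This is true, and an exploratory label could sit well with Section 9, which accepts uncorrected false positives and looks to future trials. But the synopsis goes beyond calling the study exploratory: it says there will be no formal analysis.

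**Placebo cycles are tested too, and cell function screens false positives.** Section 9.3 does mention post-placebo values against pre-dose values. But finding one dose significant and placebo not significant is not a test of their difference. The functional screen uses the same unadjusted pre/post comparison, so a time-of-day change in cell responses would pass it.

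**Conclusion.** The point holds in two parts. The synopsis sentence contradicts Sections 9.3 and 9.4, and the texts must be reconciled; this rests on the wording alone. Section 9 also lacks a dose-versus-placebo comparison, a between-dose comparison and a dose trend, in a crossover built to provide them.

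The size of the second part depends on diurnal variation, which the protocol says is unknown. Under the assumptions above, the chance of crediting an inert supplement with a rise in a given mediator runs from 1.8% with no time-of-day effect to about 82% (n = 33) or 90% (n = 40), if time of day alone matches the planning effect. These figures illustrate the exposure; they do not predict what the trial will show.

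The documents do not support the inference that the data cannot answer the dose question. The data will be collected; the analysis is not written down. It should be corrected before unblinding.

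**What to change.** 1. In the synopsis, replace the sentence ruling out formal analysis with a reference to Section 9. If the Section 9 tests are meant as exploratory, say so in both places.
2. In Section 9.4, add a within-participant comparison of change from each cycle's 0h value for each dose minus placebo, and a trend across 0, 1.5, 3.0 and 4.5 g. The model form is a choice. A mixed model with dose, period and a random participant effect would serve, on log-transformed levels if skewed. So would paired Wilcoxon tests on the differences in change for the dose-minus-placebo comparisons. State how it applies across mediators and time points, and apply it to the white cell measures as well.
3. Base the Section 9.3 choice of time point and dose on these placebo-adjusted changes, and reconcile it with the rule in 9.4 that counts significant mediators.

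Cost: protocol wording and a small amount of extra analysis. Fewer mediators may be called significant once placebo change is removed. No new samples, visits or participants are needed.

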5. INTRODUCTION

5.1 Background

Acute inflammation is the body's response to injury and/or infection that is orchestrated by mediators produced at the site where the inflammatory insult occurred and instructs white blood cell and stromal cell behavior (1-3). When this response is self-contained it is protective and leads to disposal of the inciting stimulus, clearance of white blood cells from the site, repair of damaged tissue(s) and regain of function. If the response becomes dysregulated it leads to uncontrolled white blood cell activation, tissue damage and malaise. Unbridled inflammation is widely appreciated as the unifying component in many chronic conditions including metabolic syndrome, vascular disease and rheumatoid arthritis (1-3).

The acute inflammatory response has classically been divided into two phases, initiation and resolution. The initiation phase is catalysed by local acting mediators including the essential fatty acid derived autacoids as well as cytokines and chemokines. Among these autacoids the arachidonic acid derived prostaglandins (PG; i.e. PGD₂ and PGE₂) and cysteinyl leukotrienes (LT) mediate vascular leakage, LTB₄ is a potent leukocyte chemo-attractant and thromboxane A₂ is a potent pro-thrombotic agent (4). On the other hand, the resolution phase is now appreciated to be a coordinated cellular and biochemical response that involves leukocyte trafficking to and from the site of injury/infection and production of autacoids that reprogram the immune response(s) (2).

Given the important role that pro-inflammatory mediators play in the initiation of inflammation it was thought that chronic inflammation is a result of unabated proinflammatory mediator production both at the site of inflammation and systemically (4, 5). Thus, a great deal of effort has been devoted over the last decades to identifying therapeutics that inhibit production of proinflammatory mediators (4, 5). This has led to the development of nonsteroidal anti-inflammatory drugs (NSAIDS), glucocorticoids, and disease-modifying antirheumatic drugs (DMARDs) that are widely used in the management and treatment of rheumatoid arthritis. The first two classes are primarily used to relieve symptoms, whereas DMARDs reduce or even prevent disease progression caused by unregulated inflammation when used early on (6). While these approaches are successful at controlling inflammation in the short term, the majority of anti-inflammatory therapeutics in clinical use to date have demonstrated adverse effects when administered over extended periods of time (1-3). Indeed chronic inhibition of these pro-inflammatory pathways results in gastro-intestinal barrier breakdown (7) and immune suppression amongst others (1-3). There is also significant variability in patient responsiveness to these therapeutics and their ability to limit inflammation significantly declines with disease severity (8, 9). In addition, these anti-inflammatories may also delay tissue repair and/or regeneration, thus underscoring the importance of developing alternative strategies that are able to reprogram the inflammatory response and promote tissue repair and regeneration (10). Given that under ideal conditions the body engages protective mechanisms that limit inflammation without unwanted side effects (1-3), gaining insights into these processes is of great interest.

5.2 Identification and actions of pro-resolving mediators.

Recently efforts to better understand processes that regulate the termination of the inflammatory response and the re-establishment of homeostasis, provided

mechanistic evidence that the resolution of inflammation is not simply a passive dissipation of signals but a coordinated cellular and biochemical process (11-16). Indeed, cells require signals that instruct their behaviour at the site of inflammation. Systematic analysis of inflammatory fluids collected from the site of injury/infection during self-resolving inflammation and assessment of cell trafficking at site of inflammation lead to the identification of a novel genus of local mediators that potently and stereospecifically regulate key steps in the resolution of inflammation. Thus these novel mediators produced by the body does not simply inhibit inflammation but activates resolution responses, thereby displaying both anti-inflammatory and pro-resolving actions (2, 11-16). Given that these the potent biological actions these novel molecules are coined as specialized pro-resolving mediators (SPM). The potent biological actions exerted on different components of the inflammatory response by these mediators further underscore the notion that inhibition of inflammation, or anti-inflammation, may not be the only approach to treat uncontrolled and chronic inflammation. Indeed these mediators provide evidence that under ideal conditions our body can regulate the inflammatory response by actively terminating it rather than inhibiting it, thereby sparing the immune response by repurposing the biological actions of leukocytes to re-establish homeostasis.

SPM production occurs via stereospecific conversion of essential fatty acids, including eicosapentaenoic acid (EPA), n-3 docosapentaenoic acid (DPA) and docosahexaenoic acid (DHA) by leukocyte enzymes, primarily lipoxygenases and cyclooxygenases. The omega-3 derived SPM are divided into four main families D- and E-series resolvins (Rv), protectins (PD) and maresins (MaR) and display both overlapping as well as characteristic biological actions. Each actively limits further neutrophil recruitment to the site of inflammation (1-3), they reduce chemo-attractant production and adhesion molecule expression, counter-regulate the production of pro-inflammatory mediators by regulating their formation and clearance, and promote neutrophil apoptosis and their clearance by macrophages as well as pain. In addition the maresins actively promote the repair and regeneration of damaged tissues, the protectins display potent anti-viral actions the D-series resolvins regulate B-cell antibody production and the E-series resolvins regulate T-cell and dendritic cell responses (1-3).

Studies investigating the production of these molecules during unresolved or chronic inflammatory conditions in experimental settings demonstrate that dysregulation in SPM production may be an underlying cause for disease propagation. For example in delayed or non resolving *Escherichia coli* infections SPM production becomes dysregulated leading to exacerbated local and systemic inflammation, failure of the host response to clear the invading pathogen and eventually death. Results with human tissues lend further support to this hypothesis, where SPM production is found to be dysregulated in a number of clinical settings including Alzheimer's disease and sepsis.

5.3 Fish oil supplementation to boost endogenous SPM

Evidence that chronic inflammation may result from inability of the body to produce adequate levels of SPM to counter regulate the ongoing inflammation suggests that increasing endogenous omega-3 levels may help promote SPM formation and thereby facilitate the termination of inflammation. A Pubmed search for the term 'fish oils supplementation + inflammation' yielded over 500 hits highlighting the fact that Fish oil supplementation is of general interest to both the academic and clinical fields and has been extensively studied. Animal studies using both fish oil as the main source of omega-3 essential fatty acids as well as other omega-3 enriched supplements

provide further evidence for the relationship between increased SPM production following supplementation and a reduction in inflammation (17-19). Studies with humans also indicate that fish oil supplementation may exert protective actions in chronic conditions such as rheumatoid arthritis (20) and certain cardiovascular diseases (21).

Omega-3 essential fatty acid supplementation has also been associated with increase SPM production in humans. In healthy volunteers taking 4 g of fish oil per day for three weeks plasma levels of three SPM, RvD1, RvD2 and AT-RvD1 were found to increase (22). In a separate study patients with chronic kidney disease were given 4 g of essential fatty acids and the investigators found significant increases in markers SPM pathways and RvD1 (23). In patients diagnosed with Alzheimer's or minor cognitive impairment, omega-3 fatty acid supplementation improved or stabilized cognitive function, it also lead to an increased ability of peripheral blood monocyte derived macrophages to phagocytose Amyloid β , and increase RvD1 levels (24). We recently developed a new platform that allows for the simultaneous measurement of all the pro-resolving mediators in addition to their pathway markers (>90 molecules) in human tissues. Using this platform we found that supplementation of healthy volunteers of healthy volunteers with 1 g essential fatty acids and aspirin increased plasma SPM levels, including RvD1, RvD2, RvD5 and RvE2 ((25), as early as 4 hours after intake providing the first evidence in humans that omega-3 supplementation can rapidly increases plasma SPM levels.

5.4 Rationale for the study

The relationship between omega-3 essential fatty acid supplementation, and specifically fish oil supplementation, and SPM production in humans is very poorly understood. Given that the body produces SPM from omega-3 essential fatty acids to regulate inflammation and also to repair damaged tissues, it is critical to gain further insights on how the body utilizes dietary supplementation of omega-3 fatty acids from fish oils for SPM formation. With the availability of the platform we recently developed (25) we are now in a unique position to better understand the biology of fish oil supplementation by monitoring the levels of SPM in plasma. This understanding may in turn shed light into the beneficial actions of omega-3 supplementation. It may also provide new leads for the control of excessive inflammation, as found in chronic inflammatory disorders, via dietary supplementation to exploit the body's own defense systems.

